# Summary of Treatment-Emergent Adverse Events in Subjects Treated with AlloStim $^{\rm TM}$ ITL-002-CRYO

The following table summarizes all AE regardless the causality:

| Adverse Event (CTCAEv3)         | Total # of
Subjects |       | % of Total |       | Grade 1 | Grade 2 |   | Grade 3 |   | Grade 4 | Grade 5 |   |
|---------------------------------|------------------------|-------|------------|-------|---------|---------|---|---------|---|---------|---------|---|
|                                 | n                      | %     | n          | %     | n       | %       | n | %       | n | %       | n       | % |
| Alkaline phosphatase (High)     | 25                     | 59.52 | 15         | 35.71 | 9       | 21.43   | 1 | 2.38    |   | 0       |         | 0 |
| ALT (High)                      | 16                     | 38.10 | 11         | 26.19 | 3       | 7.14    | 2 | 4.76    |   | 0       |         | 0 |
| AST (High)                      | 25                     | 59.52 | 15         | 35.71 | 7       | 16.67   | 3 | 7.14    |   | 0       |         | 0 |
| Allergy, Immunology Reaction    | 41                     | 97.62 | 40         | 95.24 | 1       | 2.38    |   | 0       |   | 0       |         | 0 |
| Anorexia/Decreased Appetite     | 7                      | 16.67 | 4          | 9.52  | 2       | 4.76    |   | 0       | 1 | 2.38    |         | 0 |
| Bilirubin (Hyperbilrubinemia)   | 8                      | 19.05 |            |       | 1       | 2.38    | 5 | 11.90   | 2 | 4.76    |         | 0 |
| Calcium (Hypocalcemia)          | 31                     | 73.81 | 21         | 50.00 | 10      | 23.81   |   | 0       |   | 0       |         | 0 |
| Calcium (Hypercalcemia)         | 2                      | 4.76  | 2          | 4.76  |         | 0       |   | 0       |   | 0       |         | 0 |
| Constipation                    | 7                      | 16.67 | 7          | 16.67 |         | 0       |   | 0       |   | 0       |         | 0 |
| Creatinine (High)               | 5                      | 11.90 | 3          | 7.14  | 2       | 4.76    |   | 0       |   | 0       |         | 0 |
| Distention/Bloating (Abdominal) | 4                      | 9.52  |            |       | 4       | 9.52    |   | 0       |   | 0       |         | 0 |
| Diarrhea                        | 8                      | 19.05 | 7          | 16.67 | 1       | 2.38    |   | 0       |   | 0       |         | 0 |
| Dizziness/Vertigo               | 6                      | 14.29 | 6          | 14.29 |         | 0       |   | 0       |   | 0       |         | 0 |
| Dyspnea (SOB)                   | 10                     | 23.81 | 2          | 4.76  | 5       | 11.90   | 2 | 4.76    | 1 | 2.38    |         | 0 |
| Dysphagia                       | 1                      | 2.38  |            |       | 1       | 2.38    |   | 0       |   | 0       |         | 0 |
| Edema (Limbs)                   | 14                     | 33.33 | 5          | 11.90 | 7       | 16.67   | 2 | 4.76    |   | 0       |         | 0 |
| Ecchymosis                      | 5                      | 11.90 | 5          | 11.90 |         | 0       |   | 0       |   | 0       |         | 0 |
| Fracture                        | 1                      | 2.38  |            |       |         | 0       | 1 | 2.38    |   | 0       |         | 0 |
| Flu-like Symptoms               | 38                     | 90.48 | 34         | 80.95 | 4       | 9.52    |   | 0       |   | 0       |         | 0 |
| Heartburn/Dyspepsia             | 3                      | 7.14  | 3          | 7.14  |         | 0       |   | 0       |   | 0       |         | 0 |
| Hemoglobin (Low)                | 34                     | 80.95 | 15         | 35.71 | 16      | 38.10   | 3 | 7.14    |   | 0       |         | 0 |
| Hypertension                    | 1                      | 2.38  | 1          | 2.38  |         |         |   | 0       |   | 0       |         | 0 |
| Hypoalbunemia (Low Albumin)     | 29                     | 69.05 | 13         | 30.95 | 12      | 28.57   | 4 | 9.52    |   | 0       |         | 0 |
| Hypotension                     | 2                      | 4.76  | 2          | 4.76  |         | 0       |   | 0       |   | 0       |         | 0 |

# Summary of Adverse Events Regardless the Causality ITL-002-CRYO
|                                    | Tota     | l # of | (112) - 1820(A) | 36 | 1.64 - 16 - 164 - | 244     |    | 578     | 9 | 16 S 51 | 162 | - 12 - 54- |
|------------------------------------|----------|--------|-----------------|-----------|-------------------|---------|----|---------|---|---------|-----|------------|
| Adverse Event (CTCAEv3)            | Subjects |        | % of Total      |           | Grade 1           | Grade 2 |    | Grade 3 |   | Grade 4 | Gr  | rade 5     |
|                                    | n        | %      | n               | %         | n                 | %       | n  | %       | n | %       | n   | %          |
| Infection/Normal ANC               | 2        | 4.76   | 1               | 2.38      | 1                 | 2.38    |    | 0       |   | 0       |     | 0          |
| Insomnia                           | 13       | 30.95  | 10              | 23.81     | 3                 | 7.14    |    | 0       |   | 0       |     | 0          |
| Leukopenia (Decreased WBC)         | 19       | 45.24  | 14              | 33.33     | 5                 | 11.90   |    | 0       |   | 0       |     | 0          |
| Lymphadenopathy                    | 15       | 35.71  | 15              | 35.71     |                   | 0       |    | 0       |   | 0       |     | 0          |
| Lymphopenia (Low Abs. Lymphs)      | 32       | 76.19  | 6               | 14.29     | 9                 | 21.43   | 16 | 38.10   | 1 | 2.38    |     | 0          |
| Mood Alteration-Agitation          | 2        | 4.76   | 2               | 4.76      |                   | 0       |    | 0       |   | 0       |     | 0          |
| Mood Alteration-Anxiety            | 4        | 9.52   | 3               | 7.14      | 1                 | 2.38    |    | 0       |   | 0       |     | 0          |
| Mood Alteration-Depression         | 1        | 2.38   |                 |           | 1                 | 2.38    |    | 0       |   | 0       |     | 0          |
| Nausea                             | 17       | 40.48  | 15              | 35.71     | 2                 | 4.76    |    | 0       |   | 0       |     | 0          |
| Neuropathy/Sensory                 | 7        | 16.67  | 3               | 7.14      | 4                 | 9.52    |    | 0       |   | 0       |     | 0          |
| Neutrophils (Low Abs. Neutrophils) | 3        | 7.14   | 2               | 4.76      | 1                 | 2.38    |    | 0       |   | 0       |     | 0          |
| Pain-NOS                           | 39       | 92.86  | 23              | 54.76     | 15                | 35.71   | 1  | 2.38    |   | 0       |     | 0          |
| Palpitations                       | 1        | 2.38   | 1               | 2.38      |                   | 0       |    | 0       |   | 0       |     | 0          |
| Platelets (Low Platelets)          | 7        | 16.67  | 5               | 11.90     | 2                 | 4.76    |    | 0       |   | 0       |     | 0          |
| Potassium (Hyperkalemia)           | 4        | 9.52   | 4               | 9.52      |                   | 0       |    | 0       |   | 0       |     | 0          |
| Potassium (Hypokalemia)            | 10       | 23.81  | 9               | 21.43     |                   | 0       | 1  | 2.38    |   | 0       |     | 0          |
| Pruritus/Itching                   | 13       | 30.95  | 13              | 30.95     |                   | 0       |    | 0       |   | 0       |     | 0          |
| Rash/Desquamation                  | 7        | 16.67  | 7               | 16.67     |                   | 0       |    | 0       |   | 0       |     | 0          |
| Sinus Bradycardia                  | 1        | 2.38   | 1               | 2.38      |                   | 0       |    | 0       |   | 0       |     | 0          |
| Sinus Tachycardia                  | 3        | 7.14   | 2               | 4.76      | 1                 | 2.38    |    | 0       |   | 0       |     | 0          |
| Sodium (Hyponatremia)              | 20       | 47.62  | 11              | 26.19     |                   | 0       | 9  | 21.43   |   | 0       |     | 0          |
| Sweating/Diaphoresis               | 12       | 28.57  | 11              | 26.19     | 1                 | 2.38    |    | 0       |   | 0       |     | 0          |
| Taste Alteration/Dysgeusia         | 3        | 7.14   | 3               | 7.14      |                   | 0       |    | 0       |   | 0       |     | 0          |
| Urinary Frequency/Urgency          | 4        | 9.52   | 4               | 9.52      |                   | 0       |    | 0       |   | 0       |     | 0          |
| Vomiting                           | 9        | 21.43  | 7               | 16.67     | 2                 | 4.76    |    | 0       |   | 0       |     | 0          |

| Summary of Auverse Events Regariness the Causanty 11L-002-CKYO |          |       |            |       |         |         |   |         |   |         |         |   |
|--|----------|-------|------------|-------|---------|---------|---|---------|---|---------|---------|---|
|  | Total    | # of  |            |       |         |         |   |         |   |         |         |   |
| Adverse Event (CTCAEv3)  | Subjects |       | % of Total |       | Grade 1 | Grade 2 |   | Grade 3 |   | Grade 4 | Grade 5 |   |
|  | n        | %     | n          | %     | n       | %       | n | %       | n | %       | n       | % |
| Vision (Blurred/Spots)   | 1        | 2.38  | 1          | 2.38  |         | 0       |   | 0       | - | 0       |         | 0 |
| Weakness   | 13       | 30.95 | 7          | 16.67 | 4       | 9.52    | 2 | 4.76    |   | 0       |         | 0 |
| Weight loss  | 5        | 11.90 | 1          | 2.38  | 4       | 9.52    |   | 0       |   | 0       |         | 0 |

# Summary of Adverse Events Regardless the Causality ITL-002-CRYO

#### **6.7. EXPECTED BENEFITS FROM THE PROPOSED STUDY**

Subjects in this study have the potential to benefit from a new approach to cancer vaccination that is designed to provide the same tumor debulking effects of non-myeloablative allogeneic bone marrow transplantation (aBMT) without the graft-versus-host-disease (GVHD) toxicity or need for a matched donor. Patients with mCRC chemotherapy-refractory disease have only the option of Regorafenib. However, this drug has little, if any, efficacy in KRAS and BRAF mutant disease

The goal of this research is to develop new treatment options for mCRC KRAS mutant and BRAF mutant patients. This approach has the potential to benefit patients that would otherwise either not be treated or would be treated with minimally effective and highly toxic Regorafenib that provides a median of only 1.1 months of survival advantage. AlloStim®, combined with a percutaneous ablation technique of a selected metastatic lesion, creates an in-situ anti-tumor vaccine customized to the patient's own tumor. The ablation causes the release of the internal contents of the tumor cells and exposes tumor-specific antigens to the immune system. AlloStim® is then injected into the ablated lesion as an adjuvant to create the necessary inflammatory environment ("danger signals") to steer the immune response to tumor-specific Th1 immunity. Accordingly, this study will provide patients suffering from a disease with an unmet medical need with access to a new class of treatment (immunotherapy) with a mechanism of action that has potential to debulk tumor and extend survival.

#### **6.8. RATIONALE FOR THE STUDY**

This study is evaluating a personalized in-situ anti-cancer vaccine combining AlloStim® and tumor ablation or AlloStim® alone. The protocol is designed to elicit a Th1 anti-tumor immune response in patients with mCRC KRAS mutant and BRAF mutant disease. Such immune response may be capable of debulking metastatic disease. Immune cell infiltration at the margins of primary colorectal disease has been correlated with longer survival in mCRC [76]. Specifically, increased infiltration of CD8+ CTL also correlated with survival [77]. In addition, colorectal cancer patients present with skewed Th1/Th2 ratios [78]and high Th1 expression has correlated with survival [79].

#### 6.8.1. Rationale for the Doses and the Dosing Regimen

In the Part 1 of the trial, the different dosing schedules will be evaluated. Assessment of different schedules should allow for better assessments of treatment safety, tolerability, and efficacy.

There are 4 phases of dosing in this study:

1. Priming phase:

Since most metastatic patients will present with polarized Th2 immunity (or depleted Th1 immunity) [78, 80, 81], the objective of the "priming" phase of the protocol is to increase the amount of circulating Th1 cells in these patients. To accomplish this objective, patients will be injected with intradermal AlloStim® cells. The allogeneic CD4+ T-cells in AlloStim® are expected to be rejected by the patient and the Th1 type cytokines produced by AlloStim® are expected to steer the rejection response to Th1 immunity, thus creating an increased pool of Th1 memory cells in the circulation specific for the alloantigens contained within AlloStim®. In other words, the patients are expected to become immune to the investigational product with a Th1 bias.

# 2. Vaccination phase:

The objective of the "vaccination" phase of the protocol for cohorts with cryoablation is to create anti-tumor specific immunity through an in-situ vaccination method. Tumor vaccines generally contain a source of tumor antigen combined with an adjuvant which promotes immune recognition and primes for development of a specific immune response against the tumor antigen. In this protocol, a source of tumor antigen is created in-situ by ablating a selected tumor lesion using the minimally-invasive technique of image guided cryoablation.

The ablation technique is designed to cause pathological death of tumor cells, releasing internal contents to the microenvironment. It is thought that necrotic cell death stimulates active cellular immunity, whereas apoptotic death stimulates immune tolerance.

The ablation procedure results in release of large amounts of tumor debris into the tumor microenvironment that serves as a source of patient-specific tumor antigens. The ablation procedure causes a pathological type of tumor killing (necrosis) that alerts the immune system and mobilizes the cells that will respond to clean up and repair the debris, including immature dendritic cells (DC) which are responsible for directing an immune response to the engulfed antigens to either Th1 or Th2.

In order to provide an adjuvant to drive correct DC maturation, AlloStim® will be injected into the necrotic center of the ablated tumor lesion within approximately ten minutes to one hour following the ablation procedure. AlloStim® cells produce large amounts of inflammatory cytokines and express surface molecules (e.g. CD40L) which are known to cause the maturation of dendritic cells and promote development of Th1 anti-tumor immunity. Further, since the patients will be immune to the alloantigens in AlloStim®, intratumoral injection (IT) is expected to elicit a potent memory response of Th1 cells to reject these allogeneic cells. All these factors are expected to serve as an adjuvant by promoting maturation of DC to prime for antitumor specific Th1 immunity.

In the cohort without cryoablation, the IV AlloStim® infusion and subsequent rejection is expected to cause release of inflammatory cytokines that will activate NK cells and memory T-cells and cause them to traffic to metastatic tumor lesions, creating an in-situ vaccination step intended to create anti-tumor specific immunity. Tumor vaccines generally contain a source of tumor antigen combined with an adjuvant which promotes immune recognition and primes for development of a specific immune response against the tumor antigen. In these schedules, a source of tumor antigen is created in-vivo by AlloStim® leading to the release of internal antigens. These factors are expected to serve as an adjuvant by promoting maturation of DC to prime for anti-tumor specific Th1 immunity.

3. Activation phase:

Intravenous infusions of AlloStim® are designed to create a "cytokine storm" of inflammatory cytokines capable of suppressing the ability of tumors to evade immune responsiveness. In addition, intravenous AlloStim® has been shown to activate host T-

cells and macrophages through CD40L-CD40 interaction and cause these activated cells to extravasate to the tissues. Since priming and vaccination are expected to increase the titer of circulating Type 1 memory cells, extravasation causes an increase in immune cell infiltration at sites of inflammation, including metastatic tumor sites. This provides a mean to maintain and support an active cellular immune response against widely disseminated tumors. However, the inflammation is non-specific such that any inflammatory lesion such as arthritic lesions, inflammatory bowel or sites of previous injury can also become inflamed or the existing inflammation becomes exacerbated.

Since tumors are known to be capable of evading Th1 immune responses, the "activation" phase of the protocol is designed to both activate the previously created immunity and to try to disable these tumor immunoavoidance mechanisms. It is known that a highly inflammatory environment can have the effect of suppressing tumor immune avoidance and breaking tolerance to the tumor antigens in much the same manner as inflammation can break tolerance to self-tissue antigens and promote autoimmunity. In order to create this inflammatory environment, AlloStim® is infused intravenously. The infusion of the foreign cells in AlloStim® is expected to cause a highly inflammatory environment as the primed immune system of the patient activates to reject these cells. In addition, the rejection of AlloStim® is expected to have the secondary effect of activating components of the host innate immune system (such as NK cells and macrophages) and activation of both allo-specific and tumorspecific Th1 cells which should initiate the cascade of immunological events necessary for systemic tumor elimination and suppressing the ability of the tumor to avoid this immune attack.

4. Booster phase:

Intravenous infusions of AlloStim® are designed to maintain the highly inflammatory environment believed to be necessary in order to maintain an active cellular immune response against the tumor and to suppress the tumor's ability to evade immune attack.

The final "booster" phase of the protocol is designed to maintain the chronic inflammatory environment to suppress tumor immunoavoidance and to maintain the activation of both innate and adaptive immunity. To meet this objective two-three intravenous infusions of AlloStim®

# 7. STUDY OBJECTIVES

#### 7.1. PRIMARY OBJECTIVES

- 1. To determine the safety of AlloStim® combined with cryoablation vs AlloStim® alone.
- 2. Determine the schedule that provides the greatest efficacy and least adverse events

#### 7.2. EXPLORATORY OBJECTIVES

1. To assess the longitudinal changes in tumor burden by RECIST and compare these changes with the histopathological analysis of corresponding biopsies (Parts 1 and 2).

2. To assess whether immune response correlates with RECIST, histopathology, plasma biomarkers and Overall Survival (OS).

# 8. STUDY DESIGN

This is a single center, open label study of CryoVaxTM personalized anti-tumor vaccine protocol combining the cryoablation of a selected metastatic lesion with intra-lesional immunotherapy compared to AlloStim® alone.

# Part 1

3 subjects will be accrued sequentially into schedule A-1 and A-2 (Part 1). After accrual of 6 subjects, up to 25 additional subjects will be accrued into the most favorable schedule (Part 2)

### Dosing Schedule A-1: Intradermal and Intravenous Dosing Combined With Cryoablation

The priming step: Subjects will receive an ID injection of AlloStim® (0.5ml) on Days 0, 7, and 14 all in different locations.

The vaccination step: Subjects will receive cryoablation and intratumor (IT) injection of AlloStim® (3 ml) on Day 21.

The activation step: Subjects will receive an IV infusion of AlloStim® (3ml) on Day 28. The booster step: Subjects will receive two (optional) IV booster infusions of AlloStim® (5ml), one on Day 56 and Day 84.

# Dosing Schedule A-2: Intradermal and Intravenous Dosing With AlloStim® alone

The priming step: Subjects will receive an ID injection of AlloStim® (0.5 ml) on Days 0, 3, 7, 10 and 14.

The vaccination step: Subjects will receive IV AlloStim® (3 ml) on Day 21.

The activation step: Subjects will receive an IV infusion of AlloStim® (3ml) on Day 28.

The booster step: Subjects will receive two IV booster infusions of AlloStim® (3ml), one on Day 49 and another on Day 77.

# **Toxicity Monitoring**

Two types of toxicity are assessed for determination of whether a Dose Limiting Toxicity (DLT) has occurred. An acute dose limiting toxicity (ADLT) is assessed within 48h of a dose administration during the priming, vaccination and activation steps of each protocol. Cumulative dose limiting toxicity (CDLT) is assessed during the complete Safety Evaluation Period including any ADLT that occurs in the booster dosing.

An ADLT is defined as the occurrence of any of the following within 48h of dosing:

- Any  $\geq$  Grade 3 local injection site reaction;
- Any  $\geq$  Grade 3 graft vs host disease;
- Any  $\geq$  Grade 3 infusion related symptoms of duration > 2 days;
- Any  $\geq$  Grade 4 infusion reaction of any duration

For any Grade 1-2 acute toxicity, the study drug administration schedule can continue to the next scheduled dose. If an ADLT is observed, the subject will be followed until the toxicity is resolved or the subject is stable. No further dosing for that subject will occur after an ADLT event

A CDLT event is defined as the occurrence of any of the following within the Safety Evaluation Period

- Any  $\geq$  Grade 3 graft vs. host disease
- Any toxicity  $\geq$  Grade 3 that is probably or definitely related to the study drug;
- Any toxicity not present at baseline that occurs at  $\geq$  Grade 4
- Any autoimmune toxicity  $\geq$  Grade 3 not present at baseline

All adverse events (AEs) and serious adverse events (SAEs), regardless of attribution to the study drug, will be coded, graded and become part of the final safety report for each cohort. The DSMB will review the safety data on each cohort and recommend whether to advance enrollment to the next cohort.

The development of any Grade 4 or greater toxicity in any subject at any time will prompt a review of safety data by the Sponsor, PI and the DSMB prior to accrual of any additional subjects. It is recognized that Grade 4 events and death can occur in this population due to disease progression. Therefore, dosing will continue for currently enrolled subjects at the occurrence of a grade 4 event according to protocol unless the PI determines the event is definitely or probably related to the study drug. If attribution is assigned to the study drug dosing will be suspended pending review by DSMB.

In accordance with the 3+3 design, three subjects will be accrued into the first dosing schedule. If during the priming, vaccination and activation steps no ADLT are observed in any of the three subjects, accrual into the next cohort is allowed. If an ADLT occurs in two of the three subjects, no further dosing is allowed. If ADLT occurs in one of the three subjects, three additional subjects will be accrued into the same cohort. If no ADLT occurs within the additional three subjects, accrual into the next cohort can begin. If an ADLT is observed in any of the additional three subjects, no further dose escalation is permitted.

The development of any DLT toxicity in  $\geq$  33% of the accumulated number of subjects in any and all dosing schedules during the Safety Evaluation Period will result in protocol discontinuation.

At the completion of the Safety Evaluation Period for all cohorts, the safety evaluation of Part 1 will be considered completed and all enrollment will be closed. Efficacy evaluation will continue monthly for each subject until death or loss to follow-up.

# Part 2

The safety and efficacy data from Part 1 will be evaluated and the favored schedule advanced to Part 2. In Part 2 of the trial, up to 25 additional subjects may be accrued.

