# **14.6.** CONCOMITANT TREATMENTS PROHIBITED AND RESTRICTED THERAPIES DURING THE STUDY

No chemotherapy or other anti-cancer treatment is allowed within the first 140 days for Schedules A1-4 subjects and 105 days for Schedule B, C, D, E and F subjects ("Study Period"). If the PI determines that a subject requires anti-cancer treatment during the Study Period, the subject data will be dropped from the protocol. The safety data will be reported but will be censored as of the treatment date. An additional subject will be accrued for each censored subject.

Subjects with bone metastases may receive palliative radiation therapy to treat pain or prevent pathological fractures during the Study Period.

Subjects experiencing anemia can be transfused as medically required (e.g., if Hgb < 9.0) at discretion of the PI. Erythropoietin may be used in continuation therapy, if indicated.

Subjects will receive medically appropriate supportive care, including treatment of pain and infection during the Study Period.

Additional IV booster infusions are allowed at the discretion of the investigator on a monthly basis after the completion of the Study Period.

Use of steroids is not allowed unless medically indicated. NSAIDs should be used as first choice and methylprednisone or SoluMedrol as next choice if anti-inflammatory medication

is deemed necessary. Inhaled steroids are allowed on study. If a subject is administered systemic steroids during the Study Period for any reason, the subject will be dropped from the study and the data will be censored from the first day of steroid administration.

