#### **15.7.** STOPPING RULES

An external DSMB will oversee this study. The investigators and representatives of the Sponsor and DSMB will review and discuss subject data for all subjects enrolled by teleconference. The DSMB could recommend stopping the clinical trial for safety purposes.

The development of dose limiting toxicity (DLT) in any subject will prompt a review of safety data by DSMB. The development of any DLT toxicity in  $\geq 33\%$  of the accumulated number of subjects at any dosing during the assessment period (28 days after last booster infusion) will result in protocol discontinuation. However, if DTLs only occur in the Activation or Booster phase, then a decision by DSMB may be made to continue enrolling subjects to receive only priming and in-situ vaccination phases.

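### The Grade 3-4 permanent-stop rule is worded for infusion reactions, so nothing clearly bars the Day 28 IV dose after a severe systemic reaction to the A-1 Day 21 intratumoral injection

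*Combined protocol and SAP*

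**What the plan says.** Section 8 (Toxicity Monitoring) has ADLT "assessed within 48h of a dose administration during the priming, vaccination and activation steps of each protocol". Its list contains a local injection-site criterion, Grade 3 or higher graft-versus-host disease (GVHD), Grade 3 or higher "infusion related symptoms of duration > 2 days", and Grade 4 or higher infusion reaction. The abstract (Section 3) gives the same list without GVHD.

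At subject level, Section 8 says "For any Grade 1-2 acute toxicity, the study drug administration schedule can continue to the next scheduled dose" and "No further dosing for that subject will occur after an ADLT event". For Grade 4 events it says "dosing will continue for currently enrolled subjects at the occurrence of a grade 4 event according to protocol unless the PI determines" that the event is probably or definitely related; in that case dosing is suspended pending DSMB review.

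Section 15.4 gives treatment guidelines for infusion reactions. At Grade 3 and at Grade 4 it orders the infusion or IV push stopped and rules out further AlloStim for that subject.

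Under Section 8 and Section 14.4.3, the A-1 Day 21 dose is a 3 ml IT injection after cryoablation. The A-2 Day 21 dose is 3 ml IV (Section 8). The abstract gives 1 ml for the A-1 IT dose. Both schedules give IV AlloStim on Day 28.

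Other safeguards do not depend on route:
- A CDLT includes any Grade 3 or higher toxicity rated probably or definitely related, and any new Grade 4 toxicity.
- A DLT in at least 33% of the "accumulated number of subjects in any and all dosing schedules during the Safety Evaluation Period will result in protocol discontinuation".
- Section 15.7: "The development of dose limiting toxicity (DLT) in any subject will prompt a review of safety data by DSMB".
- Section 14.6: "If a subject is administered systemic steroids during the Study Period for any reason, the subject will be dropped from the study".
- Section 13.2 lists a DLT event, and the investigator's judgment of the subject's condition, as reasons for which a subject may discontinue.
- Section 14.4.2 lets the physician on duty stop, delay or cancel an infusion.

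**The concern.** The assessment window covers every route, but the systemic criteria and the permanent stop name one. A subject with a severe systemic reaction on Day 21 has either a mandatory permanent stop (IV dose, A-2) or only discretionary and conditional safeguards (IT dose, A-1). The next A-1 dose is IV and comes seven days later. Section 6.8.1 expects primed subjects to mount a strong memory response to the IT dose, and says IV dosing is meant to provoke a large cytokine release. Whether a reacting subject may go on to that dose should not depend on how a site reads the word *infusion*.

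Usage elsewhere does not settle it. The product description in Section 3 separates infusion from injection, Section 11.2.2 uses *infusion* for IV and IT dosing together, and the abstract calls the A-2 Day 21 IV dose an injection.

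**Working it through.** The plan has no figure of its own to reproduce here. The check compares the rules and then counts.

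**Doses in the ADLT window (Section 8).** A-1: 3 ID (Days 0, 7, 14) + 1 IT (Day 21) + 1 IV (Day 28) = 5, of which 1 is IV. A-2: 5 ID (Days 0, 3, 7, 10, 14) + 2 IV (Days 21, 28) = 7, of which 2 are IV. Read literally and leaving GVHD aside, a systemic ADLT criterion exists for 1 of 5 doses in A-1 and 2 of 7 in A-2.

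**Six classes of Day 21 acute systemic reaction**, excluding GVHD and autoimmune events, which are CDLTs at Grade 3 whatever the attribution. The two IV columns assume the event is accepted as infusion-related.

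| Class | CDLT, any route | ADLT after IV | Section 15.4 stop after IV | ADLT or 15.4 stop after IT, literal reading |
|---|---|---|---|---|
| Grade 3, up to 2 days, possibly related | no | no | yes | no |
| Grade 3, up to 2 days, probably/definitely | yes | no | yes | no |
| Grade 3, over 2 days, possibly | no | yes | yes | no |
| Grade 3, over 2 days, probably/definitely | yes | yes | yes | no |
| Grade 4, possibly | yes | yes | yes | no |
| Grade 4, probably/definitely | yes | yes | yes | no |
| Total | 4 of 6 | 4 of 6 | 6 of 6 | 0 of 6 |

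**What is mandatory for the subject after IT.** Only the last class has a mandatory consequence for dosing: suspension pending DSMB review, with no statement that it is permanent. For Grade 4 rated possibly related, Section 8 says dosing continues. For a Grade 3 CDLT, the DSMB reviews the data and the subject may discontinue. The steroid drop would often remove the subject, since Sections 14.6 and 15.4 point to SoluMedrol-type treatment for severe reactions, but it operates only if steroids are given, and Section 14.6 makes NSAIDs the first choice.

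**33% rule.** The smallest number k of subjects with a DLT such that k/n is at least 0.33:
- n = 3: k = 1 (1/3 = 33.3%)
- n = 4: k = 2 (1/4 = 25.0%)
- n = 6: k = 2 (1/6 = 16.7%; 2/6 = 33.3%)
- n = 7: k = 3 (1/7 = 14.3%; 2/7 = 28.6%; 3/7 = 42.9%)
- n = 31 (3 + 3 + 25): k = 11 (1/31 = 3.2%; 10/31 = 32.3%; 11/31 = 35.5%)

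One CDLT therefore stops the protocol in the first three subjects but not from the fourth on. If A-1 is favoured with no cohort expansion, up to 25 of 3 + 25 = 28 A-1 subjects (89.3%) are dosed in Part 2, where a single CDLT cannot trigger the rule and protection has to come at subject level.

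**Frequency.** The documents give no rate for systemic reactions to IT dosing. The Section 6.6.1 tables for ITL-002-CRYO show 0 of 42 subjects with Grade 3-4 allergy/immunology or flu-like events; that trial gave IT doses of 1-6 x 10^7 cells (Appendix 3). The exact one-sided 95% upper limit for 0 of 42 is 1 - 0.05^(1/42) = 6.9%, for those two terms only.

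**The case against.** The strongest reply is that *infusion* is not used strictly in this protocol. IV doses are a push over about five minutes, one IV dose is called an injection, and the vital-signs section uses *infusion* for IT as well. The Grade 1-2 sentence names no route and allows continuation only at those grades, which favours counting IT reactions. The sentence on continuing after Grade 4 events is justified by disease progression, not by acute reactions within 48 hours. All of this stands, and it makes the inclusive reading plausible. It does not make it a rule: two sites could still differ on the Day 28 dose.

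The safeguards are also real. Serious events reach the sponsor within 24 hours and the DSMB automatically, the DSMB reviews each cohort, and the physician on duty can cancel an infusion. These make an unsafe Day 28 dose less likely, but none is a mandatory bar.

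A reader might infer that the 3+3 could pass an unsafe A-1 schedule. At an assumed 33% reaction rate, A-1 clears the 3+3 with probability q^3 + 3pq^2 x q^3 = 0.434 if reactions count (p = 0.33, q = 0.67) and 1.000 if they do not. That contrast ignores the 33% rule. For reactions that are CDLTs, any one in the first three subjects stops the protocol, so the chance of proceeding is q^3 = 0.67^3 = 0.301 on either reading. The Section 15.7 exception for DLTs confined to activation or booster does not reach Day 21.

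A reader might also infer a clear route difference for Grade 3 reactions over two days rated possibly related, which are neither ADLT nor CDLT after IT. But *infusion related* is itself a causal judgment, so an event rated only possibly related might not be accepted as an ADLT after IV either.

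**Conclusion.** The concern holds as a subject-level safety gap. As written, no mandatory rule clearly bars an A-1 subject with a Grade 3-4 acute systemic reaction to the Day 21 IT injection from the Day 28 IV dose, while the same reaction to an IV dose is a permanent stop. The gap is clearest for Grade 4 reactions rated only possibly related, and for Grade 3 reactions not treated with steroids. It matters most after the first three subjects, when one CDLT no longer reaches 33%.

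The documents do not support three larger claims that a reader might draw: that IT reactions go uncounted for safety (four of six classes are CDLTs), that the 3+3 is materially weakened, or that the safety comparison is tilted towards A-1. The class counts are unweighted and are not event rates.

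The conclusion rests on the literal reading of *infusion* being a reasonable one, and on A-1 being the first cohort. Such reactions may be rare, so this is a cheap improvement rather than a flaw that undermines the design.

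**What to change.** 1. **Section 15.4:** apply the Grade 3 and Grade 4 no-further-AlloStim rule to *an acute systemic reaction to the study drug after any ID, IT or IV dose*.
2. **Section 8, Toxicity Monitoring:** state that this rule overrides the provision for continued dosing at a Grade 4 event. Put the same statement beside the matching text in the abstract.
3. **ADLT lists in Section 3 and Section 8:** replace the two infusion terms with the same phrase, keep the thresholds (Grade 3 lasting over 2 days; Grade 4 of any duration), and list Grade 3 or higher GVHD in both.
4. **DLT form:** match the wording.

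No visits or procedures are added. The costs are a few more ADLTs in either schedule, including after ID doses, and the loss of the Day 28 dose for some A-1 subjects.

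The sponsor should also accept knowingly that one added ADLT among the first three subjects meets the 33% discontinuation rule. Of the four classes that would become ADLTs after IT, three are already CDLTs. The only class newly counted as a DLT is Grade 3 lasting over 2 days and rated possibly related, which can arise on a day when cryoablation is a competing cause.
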